
B. State the purpose of the study:

Primary Aim 1.1: Dose optimization, open-label trial to determine the proportion of subjects with SCI with a normotensive response to droxidopa (Efficacy #1). Normotension will be defined as an average systolic BP (SBP) recorded 60-120 minutes after dose administration of 111-139 mmHg in males and 101-139 mmHg in females or a maximum dose of 800 mg is reached without adequate SBP response.

Primary Aim 1.2: Dose optimization, open-label trial to determine the proportion of subjects with SCI with a hypertensive response to droxidopa (Safety #1). Hypertension will be defined as a sustained elevation (≥ 30 consecutive minutes)

in seated SBP \geq 140/100 mmHg or intolerable side effects considered related to study medication.

Secondary Aims: To determine the effect of the individualized optimal dose of droxidopa, compared to placebo, on (1) supine BP (Safety #2), (2) SBP during a head-up tilt (HUT) maneuver to 70° (Efficacy #2) and change in cerebral blood flow velocity (CBFv) from supine to HUT (Efficacy #3).

C. Background of Study Population - Clinical Information:

- a. Describe the general population from which you plan to recruit subjects for this study (i.e., Demographics of potential subjects):

All eligible participants, including women and minorities, will be included in this investigation if they demonstrate an understanding of the study procedures, meet entrance criteria, and sign the informed consent. Individuals will be recruited from prior study participation and referral from primary physicians.

- b. Describe the medical condition in this population:

Subjects have experienced a spinal cord injury, experienced muscle paralysis below the level of injury, and have a variety of secondary medical consequences such as cardiovascular disease, pressure ulcers, osteoporosis, and diabetes. In addition, it is not uncommon for them to have received an initial dual diagnosis of traumatic brain injury and SCI.

- c. How does this condition affect this population (symptoms)? Depending on the level of injury subjects may have blood pressure dysregulation, elevated resting heart rate, reduced blood flow to the brain, and impaired cognitive function in addition to decreased levels of upper and/or lower body sensory and motor function.

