- d. Does this population have an understanding or knowledge of the medical condition being studied? Many of the subjects who have been injured longer do have an understanding of their injury and the problems associated with it. Subjects who are acutely injured may not have been provided with a vast amount of knowledge on their injury but they will not be recruited for this study.

- e. What is the traditional treatment provided for this condition?

Traditional treatments address the secondary medical consequences of SCI via prevention and specific organ system therapies. Some individuals undergo experimental therapies in an effort to regain function.

- f. Explain how special needs that may arise with this population due to this medical condition are addressed (e.g. Additional care provided, supportive therapy, physiotherapy, behavioral therapy):

We accommodate subjects as best as possible by providing physical assistance for transferring, preparing for the study, and completing study-related paperwork. In addition, all our resources (i.e., bathroom, desks and doors) are wheelchair accessible.

- g. Describe how research subjects will be referred for appropriate care while they are enrolled in the study? **If, and when necessary, all participants will be referred to the appropriate clinical personnel given the medical concern presented.**
- h. Describe whether providers (all clinical staff) have experience in providing care to subjects: **There are several physicians at the site that have been board certified for a number of years and have excellent experience.**
- i. Does the James J. Peters VAMC have the appropriate medical or psychosocial resources required for any emergency needs for research subjects? **The JJPVAMC is an SCI center and cares for more than 300 veterans with SCI as both in-patients and outpatients; medical resources are available if emergently required.**

4. Selection of subjects:

- a. Indicate number of subjects to be enrolled at this site (**Total # of subjects approved by IRB**):

A total of 75 subjects will be screened (25 at JJPVAMC; 25 at ISMMS; 25 at KF). Of those 75 screened, 60 eligible subjects will be enrolled for study 1 (20 at JJPVAM; 20 at ISMMS; 20 at KF). From those 60 who complete study 1, A total of 30 will be enrolled for study 2 between all sites.

- b. Indicate total number of subjects to be enrolled, if multisite study:

A total of 75 subjects will be screened. (25 at JJPVAMC; 25 at ISMMS; 25 at KF)

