d. Justify any exclusion of specific gender, age, and racial or ethnic groups:

N/A

6. State inclusion criteria for enrollment in study:

Study 1:

- 1) Male or Female, age 18 to 89 with traumatic SCI.
- 2) SCI Subjects (n=40):
 - a) Any level of injury;
 - b) Any AIS grade of SCI;

- c) Non-ventilator dependent
- d) Primarily wheelchair dependent for mobility;
- e) Duration of injury < 1 year

3) Low Blood Pressure:

Systolic BP less than 110 mmHg and/or diastolic BP less than 70 mmHg for males;
Systolic BP less than 100 mmHg and/or diastolic BP less than 70 mmHg for females;

4) Primary Language is English.

Able to provide informed consent

Study 2:

5) Male or Female, age 18 to 89 with traumatic SCI.

6) SCI Subjects (n=40):

- a) Any level of injury;
- b) Any AIS grade of SCI;
- c) Non-ventilator dependent
- d) Primarily wheelchair dependent for mobility;
- e) Duration of injury < 1 year

7) Low Blood Pressure:

Systolic BP less than 110 mmHg and/or diastolic BP less than 70 mmHg for males;
Systolic BP less than 100 mmHg and/or diastolic BP less than 70 mmHg for females;

8) Primary Language is English.

Able to provide informed consent

9) Showed a normotensive blood pressure in response to Droxidopa during study 1.

7. State exclusion criteria for enrollment in study:

Study 1 and Study 2:

- Current illness or infection
- Individuals with frequent or severe autonomic dysreflexia
 - a. More than 3 symptomatic events per week
 - b. BP \geq 140/90 mmHg
 - c. Significant adverse subjective symptoms reporting
- Hypertension
- Any neurological condition other than SCI (Alzheimer's disease, dementia, stroke, multiple sclerosis, Parkinson's disease, etc.)
- History of epilepsy or other seizure disorder
- History of traumatic brain injury (TBI)
- Liver or kidney disease
- Bladder problems including blockage of the urine and/or weak urine stream.
- Diagnosis of a psychiatric disorder such as schizophrenia or bipolar disorder
- Known artery disease, heart failure, AV block, and irregular heartbeat
- Any allergies to droxidopa, aspirin, polyethylene oxide, polyethylene glycol, hydroxypropyl cellulose, butylated hydroxytoluene, magnesium stearate, hypromellose, yellow ferric oxide, and red ferric oxide
- Major surgery in the last 30 days
- Illicit drug abuse in the past 6 months
- Pregnant
- Your prescription medications will be reviewed by the study investigators and research staff.

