c. What special safety precautions are utilized to minimize risk of coercion to protect the rights and welfare of these subjects [e.g., avoid financial incentives, consult with patient advocates or representatives]? **Participants will be given many opportunities to ask questions and to review the consent with their primary care physicians.**

10. As PI, do you have access to sufficient population that will allow recruitment of the necessary number of subjects?

YES	X	NO
------------	----------	-----------

11. Indicate how potential subjects will be recruited:

Potential participants will be recruited via primary care referral from a KF, ISMMS or JJP VAMC care provider or from prior enrollment in a research study. All subjects will be recruited in accordance with HIPAA and local IRB guidelines by the co-investigator by telephone or on the day of their regularly scheduled appointment.

12. Description of the Consent Process:

- a. Describe the enrollment procedures for participation in the study:
Participants contact or are referred to a Co-investigator at KF, ISMMS and JJP VAMC and will provide information relative to the inclusion criteria. If the participant displays interest in participating, the co-investigator will thoroughly review the consent documents, and after the consent process is complete a testing date is scheduled.

- b. Indicate when and where consent will be obtained:

The informed consent process will be conducted in the privacy of the research laboratory at a time that is convenient for the participant and research staff, prior to initiation of study procedures.

c. Who will conduct the consent interview?

Research staff members associated with the research protocol as listed on the assurance page will conduct the consent interview.

d. Will a legally authorized representative provide consent or permission for a subject, as appropriate?

YES	X	NO	
------------	----------	-----------	--

e. What is the waiting period between informing the prospective subject about the study and obtaining consent?

There is no defined waiting time between completion of the informed consent process and initiating study procedures. However, the informed consent process will be completed prior to initiating study procedures.

Time devoted to consent discussion? The participant will be given adequate time to read the consent and ask questions. As long as necessary.

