Safety information will be collected in the 1) case report forms, 2) study visit documents, and 3) via telephone follow-up calls. All data will be monitored. Data will be collected during scheduled study visits (weekly). Cumulative data will be reviewed on a monthly basis.

d. Describe how you will determine whether the study should be continued in light of emerging information:

If the current risk/benefit ratio shifts at any time during the study, the research protocol will be modified or discontinued immediately.

e. Is there a Data Monitoring Committee (DMC) or a Data Safety Monitoring Board (DSMB)?

DMC		DSMB		NO	X
-----	--	------	--	----	---

If no, proceed to question 17.

Describe your DMC or DSMB, including frequency of reporting:

Describe how the DMC or DSMB will communicate with the IRB:

17. Data Analysis and Sample Size:

a. Describe the analysis that will be performed on the data:

Primary Aim 1.1: Dose optimization, open-label trial to determine the proportion of subjects with SCI with a normotensive response to droxidopa (Efficacy #1). Normotension will be defined as an average systolic BP (SBP) recorded 60-120 minutes after dose administration of between 111-139 mmHg in males and 101-139 mmHg in females.

•Hypothesis 1.1 – Seated SBP will be normalized in 60% of the study sample following administration of droxidopa.

- This hypothesis will be tested by constructing a 95% confidence interval about the sample proportion of cases in which BP is normalized with

droxidopa. The inclusion of the 60% value in the confidence interval will be taken as evidence in support of the hypothesis. Further, the point estimate and confidence interval will provide the first reported estimate of the BP normalizing effect of droxidopa in the population with SCI.

Primary Aim 1.2: Dose optimization, open-label trial to determine the proportion of subjects with SCI with a hypertensive response to droxidopa (Safety #1). Hypertension will be defined as a sustained elevation in seated SBP $\geq 140/100$ mmHg or intolerable side effects considered related to study medication

•**Hypothesis 1.2 – Less than 10% of the study sample will exhibit hypertension or intolerable side effects related to administration of droxidopa.**

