- This hypothesis will be tested by constructing a 95% confidence interval about the proportion of cases in which either seated BP $\geq 140/100$ or intolerable side effects occur. If the 95% CI excludes values $\geq 10\%$, this will be taken as evidence in support of the hypothesis. Further, the point estimate and confidence interval will provide the first reported estimate of the expected side effects of droxidopa treatment in the population with SCI.

Secondary Aims: To determine the effect of the individualized optimal dose of droxidopa, compared to placebo, on (1) supine BP (Safety #2), (2) SBP during a head-up tilt (HUT) maneuver to 70° (Efficacy #2) and change in cerebral blood flow velocity (CBFv) from supine to HUT (Efficacy #3). The following hypotheses will be tested in hypotensive individuals with SCI:

•**Hypothesis 2.1A – Average supine SBP will be significantly increased following droxidopa administration compared to placebo.**

- This hypothesis will be tested using a repeated measures analysis of covariance where the pre-droxidopa or placebo SBP will be used as the covariate and the adjusted post-test scores will serve as the dependent variable. In addition, the covariate adjusted point estimate and 95% confidence interval of the difference between drug conditions will provide the first reported estimate of the supine SBP response to droxidopa versus placebo in the SCI population.

•**Hypothesis 2.1B – The proportion of supine BP observations $\geq 140/100$ mmHg following droxidopa administration will not differ significantly from the proportion observed during the placebo trial.**

- This hypothesis will be tested by performing separate (one each for systolic and diastolic pressure) tests of the differences between dependent proportions, from which the 95% confidence intervals will be calculated. The presence of zero in a confidence interval will indicate a lack of statistical difference in incidence of hypertensive events between the droxidopa and placebo conditions.

•**Hypothesis 2.2 – Average SBP during 70° HUT will be significantly increased following droxidopa administration compared to placebo.**

- This hypothesis will be tested by performing a dependent t-test between the mean SBP during 70° HUT comparing droxidopa to placebo. Further, the point estimate and resulting 95% confidence interval will provide an estimate of the SBP response to HUT of droxidopa versus placebo in the SCI population.

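### Both inclusion lists admit only people injured for under 1 year, yet the same form says acutely injured people, a group given no time limit, will not be recruited

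*Combined protocol and SAP*

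**What the plan says.** Item 6 of the Combined protocol and SAP gives separate inclusion lists for Study 1 and Study 2. Criterion e) is the same in both (items 2e and 6e): "Duration of injury < 1 year". The exclusion list in item 7 applies to both studies and contains no criterion on time since injury. The item closest to one excludes major surgery in the last 30 days.

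Section C.d of the same form asks what the study population knows about its condition. The answer says: "Subjects who are acutely injured may not have been provided with a vast amount of knowledge on their injury but they will not be recruited". The sentence before it describes the other group: "Many of the subjects who have been injured longer do have an understanding of their injury".

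On the source of participants, section C.a says "Individuals will be recruited from prior study participation and referral from primary physicians", and item 11 again names referral by a care provider "or from prior enrollment in a research study".

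Item 17.a describes what the two primary analyses will deliver. Hypothesis 1.1 is to give the "first reported estimate of the BP normalizing effect of droxidopa in the population with SCI", and Hypothesis 1.2 the "first reported estimate of the expected side effects of droxidopa treatment in the population with SCI".

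**The concern.** The eligibility lists and the recruitment statement point in different directions. Section C.d leads a reader to expect people well past their injury. The lists restrict entry to the first year and put no lower limit on time since injury.

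The stake is the population behind both primary estimates. Aims 1.1 and 1.2 are single proportions with confidence intervals in the Study 1 participants, with no control group. Their meaning therefore depends directly on who was eligible. If the printed criterion is applied, nobody injured for 1 year or more contributes to the normotensive or the hypertensive proportion, although the form presents both as estimates for people with SCI in general. Item 17.b adds that the results will be used to power a larger trial, so an unintended population would carry forward into that design.

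**Working it through.** No sample size, power or error rate is involved, so the check is a comparison of texts.

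**Step 1: is acute defined?** Neither supplied document gives a time limit for acute. Outside section C.d the word appears only in accounts of earlier reports and in reference titles. *Injured longer* in C.d is not tied to 1 year.

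**Step 2: apply each text to each group.** Let the undefined acute phase end at some time *a* after injury, with *a* greater than 0 and at most 1 year.

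| Time since injury | Item 6 criterion e) and item 7 exclusions | Section C.d |
|---|---|---|
| Less than *a* | Passes criterion e); no duration exclusion applies | Not to be recruited |
| From *a* to under 1 year | Passes criterion e) | Not ruled out |
| 1 year or more | Fails criterion e) | Not ruled out |

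The first row is a mismatch for every positive value of *a*: the lists let in people the form says it will not recruit. The second row is the only group acceptable to both texts. Its width depends on *a*, and it is empty if acute means the whole first year. The third row is barred by the lists whatever *a* is.

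**Step 3: try the opposite inequality.** If criterion e) required more than 1 year, the first and second rows would be barred and the third admitted. The lists would then carry out the C.d statement for any *a* up to 1 year. That reading fits two other facts. Recruitment draws partly on earlier study participants (C.a and item 11). The group's earlier droxidopa dose-escalation trial was in people with chronic SCI (Protocol, Anti-Hypotensive Treatment in SCI). This shows that the opposite sign would be coherent. It does not show that it was intended.

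**Step 4: look for another text that settles it.** The Protocol's Screening Visit paragraph sets blood pressure and orthostatic criteria and mentions no duration of injury. It is not a complete eligibility list: the Study Population paragraph refers to Human Subjects Form 11 for the full description, and that form is not among the documents. The Protocol therefore neither confirms nor contradicts criterion e).

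**The case against.** The strongest reply is that there is no logical contradiction. People past the acute phase but still within the first year meet both texts. Section C.d answers a question about patients' knowledge and is not itself an eligibility rule. This stands as far as it goes: the texts are not strictly incompatible. It does not remove the problem, because neither list contains the lower limit that such a window would need, and C.d is a plain statement to the IRB about who will not be recruited.

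A reader might go further and infer that the sign is certainly reversed. The documents do not support that. The population of an earlier trial does not bind this one, and prior study participation is only one of two recruitment routes. The repetition of the line says little about intent, since the Study 2 list largely repeats the Study 1 list. Nor can a fault in text conversion be wholly excluded, although the sign is the same in both places and other inequality signs in the form came through. The source file would settle that, but acute would still be undefined.

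A reader might also infer that a wrong sign would turn people away at first contact and leave no trace in the screening log, since item 12.a says that people "will provide information relative to the inclusion criteria" before the consent review. The form does not say that anyone is rejected at that stage. The Protocol determines eligibility at a consented screening visit where medical history is taken, so a failure on duration could be recorded there.

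It is fair to add that the population claim in item 17.a is loose in other ways: entrants must also have low blood pressure and traumatic injury and be mainly wheelchair dependent. Duration still differs, because on this criterion the form's own texts pull apart.

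Finally, Human Subjects Form 11 may contain a definition of acute. It cannot be assumed to cure a mismatch inside this form.

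**Conclusion.** The point holds as an inconsistency in the written eligibility criteria and must be fixed. As printed, both lists bar everyone injured for 1 year or more and fail to bar the acutely injured people whom the form says it will not recruit. This affects every participant in both primary proportions and in Study 2.

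Confidence is high for the inconsistency only. The direction of the error, if there is one, is open: a reversed inequality is plausible and unproven. No effect on enrolment or on either primary proportion can be calculated, because the documents give neither a cut-off for acute nor a distribution of time since injury. The conclusion rests on the item 6 lists being applied as written and on the documents supplied.

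**What to change.** The sponsor should:

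- reconcile criterion e) in both lists of item 6 with section C.d, and confirm or correct the direction of the inequality in each list;
- state *acutely injured* as a time since injury;
- use one duration criterion in every eligibility text, including Human Subjects Form 11;
- if under 1 year is intended, restrict the population named for Aims 1.1 and 1.2 in item 17.a, and the matching text in the Protocol's Data Analysis section, to people within that limit.

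The cost is a set of text changes submitted as an IRB amendment, plus a check of eligibility records for anyone already assessed under the printed criterion. No extra participants, visits or procedures are needed to make the texts agree.
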